## Study protocol

### Patient population and randomization

The present study included patients for whom COL was planned with 1) cervical myelopathy at 3 or more levels due to spondylosis, congenital stenosis, or OPLL; 2) aged more than 20 years; and 3) with American Society of Anesthesiology physical status class 1 or 2. The exclusion criteria were as follows: 1) concomitant neurological disease such as cerebral palsy or amyotrophic lateral sclerosis; 2) concurrent cancer or infection; 3) previous cervical spinal surgery; 4) a trauma-associated lesion; 5) inability to be followed up; and 6) refusal to participate in the study. The proportions of fusion failure were assumed to 30% and 10% in laminoplasty with a conventional drill and with a UBS. To provide a power of 80% with a two-tailed significance level of 0.05, 72 patients for each surgical method were required. Considering a drop-out rate of 25%, 95 patients in each group were enrolled. A computer-generated variable randomized block design was used for randomization and a research nurse independent of this trial provided randomization with concealed assignment. A total of 190 patients were equally allocated to one of two treatments (Fig. 1). The attending surgeons, patients, and staff members in the operating room were blinded to the surgical method until the day of surgery. Recruitment of patients started in July 2015 and ended in February 2018.

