### Statistical analysis

Continuous data were summarized as mean or median (min, max) values depending on normality. Categorical variables are summarized as frequency (%). The analysis for the primary outcome was performed on data from the intention-to-treat population, which included all subjects who were randomized. Since about 14% of subjects missed the CT to assess bone union at 6 months, multiple imputation was applied. Five multiply-imputed data sets were created using a monotone logistic regression model. The variables in Table 1 were included in the imputation model. A sensitivity analysis was performed with the subjects who received a CT scan at 6 months, who were defined as the per-protocol population. The union rate was compared between the drill group and the UBS group using logistic regression. Because each subject had several laminae, logistic regression with the robust sandwich covariance estimate was used to account for the correlation among laminae within a subject.

Secondary outcomes were compared using the chi-square test for non-continuous values and the t-test or Wilcoxon rank-sum test for continuous values. A linear mixed model was used for clinical outcomes to evaluate between-group differences and changes during each postoperative period compared to the preoperative point, and adjusted p-values were evaluated using the Bonferroni method. The fixed effects were group, time, and the interaction between group and time. All statistical analyses were performed using SAS version 9.4 (SAS Institute, Cary, NC, USA), and statistical significance was defined as  $p < 0.05$  (two-sided).

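### Bonferroni adjustment of the mixed-model clinical outcomes is valid, but Holm's step-down procedure would keep more power on these secondary outcomes at the same 5% familywise error, and the family being adjusted is not defined

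*Combined protocol and SAP*

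**What the plan says.** The Statistical analysis section uses a linear mixed model for the clinical outcomes to "evaluate between-group differences and changes during each postoperative period compared to the preoperative point". The model terms are given: "The fixed effects were group, time, and the interaction between group and time". On multiplicity the section says only that "adjusted p-values were evaluated using the Bonferroni method", with a two-sided 0.05 threshold for significance. No step-down or other sequential procedure is named. The section does not state how many comparisons enter the adjustment, or whether the between-group contrasts and the changes from the preoperative point are adjusted together or apart.

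The sample size in Patient population and randomization was set for fusion failure alone: "The proportions of fusion failure were assumed to 30% and 10% in laminoplasty with a conventional drill and with a UBS", and "To provide a power of 80% with a two-tailed significance level of 0.05, 72 patients for each surgical method were required". No power is claimed for the clinical outcomes.

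**The concern.** Bonferroni tests each of m hypotheses at 0.05/m. Holm orders the p-values and tests the smallest at 0.05/m, the next at 0.05/(m−1), and so on, stopping at the first failure. It needs no assumption beyond those of Bonferroni and gives the same familywise guarantee. Every threshold is at least as large, so Holm never loses a rejection. Keeping Bonferroni therefore gives up some power for no gain in error control.

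The undefined family adds to this. Both arms undergo laminoplasty and differ in the cutting instrument, so improvement after surgery is to be expected in each arm and says nothing about drill versus UBS. If those within-arm changes were counted, they would raise the divisor for the contrasts that randomisation supports.

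At stake is how many visits show a significant between-group difference on a secondary clinical outcome. The primary union analysis and its sample size are not touched.

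**Working it through.** **The plan's own figure.** For 30% versus 10%, two-sided 0.05 and 80% power, the standard two-proportion formula gives 62 per group, or 72 with continuity correction, which matches the plan. Then 72/0.75 = 96, against the stated 95. This confirms the design alpha and shows that the trial was sized for fusion failure only.

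**Inputs for the comparison.** The two-sided 0.05 level and the Bonferroni method come from the Statistical analysis section. The rest is assumed, because the available text gives none of it:
- K = 3 to 5 postoperative visits.
- 82 per arm, from 95 × 0.86 = 81.7. The 14% is the share missing the 6-month CT, borrowed here as a stand-in for clinical follow-up.
- A true between-group difference of 0.45 SD at every visit.
- Correlation of 0.4 to 0.8 between visits.

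**Bonferroni power per visit.** The mean of each z-statistic is 0.45 × √(82/2) = 2.88. Power at one visit is the probability that a normal variable with this mean exceeds the two-sided critical value for 0.05/m.
- m = 4: 0.05/4 = 0.0125, power 64.8%.
- m = 12 (4 between-group contrasts plus 2 × 4 = 8 within-arm changes): 0.05/12 = 0.0042, power 50.6%.

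**Holm.** With K = 4 the thresholds are 0.0125, 0.0167, 0.025 and 0.05. Average per-visit power by simulation of correlated z-statistics, in percent:

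| Family | Bonferroni | Holm | Gain, points |
|---|---|---|---|
| Between-group only, K = 4, correlation 0.6 | 64.8 | 73.4 | 8.6 |
| Pooled with within-arm changes, K = 4, correlation 0.6 | 50.6 | 73.6 | 23.0 |
| Between-group only, all scenarios | 62–69 | 70–77 | about 6–10 |
| Pooled, all scenarios | 48–54 | 70–77 | about 21–24 |

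The pooled rows take all 2K within-arm changes as certain to be rejected.

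**Where the pooled shortfall comes from (K = 4, correlation 0.6).** Separating the families with Bonferroni kept gives 64.8 − 50.6 = 14.2 points. Applying Holm within the separated family adds 73.4 − 64.8 = 8.6 points.

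**Limits of the gain.** Holm's first threshold equals Bonferroni's. In the between-group family the chance of at least one significant visit is therefore identical: 87.6% for both at K = 4, correlation 0.6. The gain is on the second and later visits, and it is near zero if only one visit differs.

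**Error control.** With no between-group difference, Bonferroni's actual familywise error for the between-group contrasts is about 3.0 to 4.6% in the separate family and 1.1 to 1.6% in the pooled one. Holm in the pooled family stays between 3.0% and 4.7%, within the 5% limit.

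**Sensitivity.** With K = 3 to 6, 71 (95 × 0.75) or 95 per arm, differences of 0.3 to 0.5 SD and correlation 0.5, Holm gains about 4 to 10 points in the separate family and 13 to 25 in the pooled one. It kept every Bonferroni rejection in every scenario.

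**The case against.** The best defence is that Bonferroni is valid, transparent and comes with matching simultaneous intervals, which Holm does not offer in simple form. That stands: this is lost efficiency in secondary outcomes, with no inflation of type I error. The section promises no simultaneous intervals, however, so nothing it commits to would be lost.

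A reader might infer that the plan pools pre-to-post changes with between-group differences and so loses more than 20 points of power. The documents do not support this. One sentence mentions both kinds of comparison and then Bonferroni, but it defines no family. The larger figure also needs every within-arm change to be significant.

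A reader might also infer that a real drill-versus-UBS difference on an outcome is likelier to be missed altogether. In a between-group family that is wrong, because the chance of at least one significant visit is the same under both methods.

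The size also rests on generous inputs. Nothing in the documents supports a 0.45 SD difference sustained at every visit, and CT missingness is not clinical-outcome missingness. This limits the size of the gain but not its direction, which is a theorem.

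Finally, the text is in the past tense, reports observed CT missingness and gives February 2018 as the end of recruitment. A move to a less conservative adjustment may come after the data are known. That objection stands and belongs in the cost.

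**Conclusion.** The point holds as a cheap improvement to the secondary analysis. Bonferroni is not an error, but Holm does at least as well under any dependence between contrasts, at the same 5% familywise error.

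Under the assumptions listed, the gain is about 6 to 10 points of average per-visit between-group power if the family is the between-group contrasts, confined to second and later significant visits. The figure of 21 to 24 points is conditional on a pooled family that the plan neither states nor rules out, and most of it is due to the family rather than to the choice of Bonferroni. Stating the family is therefore worth as much as naming Holm. The primary union result is unaffected.

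**What to change.** In the Statistical analysis section, replace the Bonferroni method with the Holm step-down method. Define the family, separately for each clinical outcome, as the K postoperative between-group contrasts, and state K. Report within-arm changes from the preoperative point as estimates with confidence intervals, outside that family.

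In SAS 9.4, which the plan already uses, this means requesting the K contrasts from the mixed model and passing their p-values to PROC MULTTEST with the HOLM option. A default simultaneous adjustment over all group-by-time cell means is not a substitute: it covers every pair of cells and can disagree with the Holm p-values.

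The cost is a sentence or two in the plan and one extra SAS step. Holm has no simple matching simultaneous intervals, so unadjusted intervals would accompany the adjusted p-values and should be labelled as such. If the change is made after outcome data have been seen, both the new method and the family definition must be disclosed as post hoc. Giving the Bonferroni-adjusted values alongside would let readers see whether any conclusion depends on the change.

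### Secondary clinical outcomes: the mixed model does not adjust for the preoperative score, so its valid between-group contrasts are less precise than the data allow

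*Combined protocol and SAP*

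**What the plan says.** The Statistical analysis section describes the model for these outcomes as follows: "A linear mixed model was used for clinical outcomes to evaluate between-group differences and changes during each postoperative period compared to the preoperative point". It then lists the model terms: "The fixed effects were group, time, and the interaction between group and time". For multiplicity, "adjusted p-values were evaluated using the Bonferroni method".

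The section does not say whether the preoperative score is one level of the time factor or is subtracted to form a change score. It names no preoperative covariate, no constraint on the preoperative means, no covariance structure and no analysis population for this model. The primary outcome is handled separately: "The union rate was compared between the drill group and the UBS group using logistic regression". This point does not touch that analysis.

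**The concern.** The reference to the preoperative point shows that a preoperative score exists for these outcomes. It is natural to assume that a mixed model holding that score as a response already adjusts for it. It does not when group and group-by-time are both unrestricted: the preoperative group difference is then one more parameter to estimate. The between-group contrast at a postoperative visit is either the plain difference at that visit or the difference in change. A change score analysed at postoperative visits only is not regression-adjusted either.

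What is at stake is precision. Intervals for the between-group differences are wider than the same data could give, and the estimates move more with chance preoperative imbalance. Bias and Type I error are not in question. The trial was sized on fusion failure, and no power or decision rule is stated for the clinical scores.

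**Working it through.** **The plan's own figure.** There is no sample size for the clinical outcomes. The per-group number used below comes from the primary outcome: failure 30% against 10%, 80% power, two-sided 0.05.

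- Without continuity correction: n = [1.96·√(2×0.2×0.8) + 0.842·√(0.3×0.7 + 0.1×0.9)]² / 0.2² = 61.6, so 62.
- With continuity correction: (61.6/4)·[1 + √(1 + 4/(61.6×0.2))]² = 71.2, so 72, as stated.
- Drop-out: 72/0.75 = 96, against the plan's 95: "Considering a drop-out rate of 25%, 95 patients in each group were enrolled". The difference of one patient is immaterial here.

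**Inputs.**

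- From the documents: n = 95 per group, randomised 1:1.
- Assumed: correlation ρ between preoperative and postoperative score of 0.3, 0.5 or 0.7; equal SD σ at both times; one follow-up visit; follow-up missing completely at random; preoperative score present for everyone.
- Observed fraction p at follow-up: 1, 0.86 or 0.75. Missingness of the clinical scores is not stated, so two figures stand in for it. One is the CT figure ("Since about 14% of subjects missed the CT to assess bone union at 6 months, multiple imputation was applied") and the other is the planned 25% drop-out.

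**Variance of the between-group contrast, in units of 2σ²/n.**

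- Common preoperative mean: (1−ρ²)/p
- Free preoperative means, difference at the visit: (1−ρ²)/p + ρ²
- Free preoperative means, difference in change: (1−ρ²)/p + (1−ρ)²
- Change score as the response at postoperative visits only: 2(1−ρ)/p

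With complete data the second is 1 and the third is 2(1−ρ). The first is smaller than both for any ρ strictly between 0 and 1.

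**Ratio of the common-mean variance to the unadjusted variance.**

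| Follow-up observed | Against visit difference, ρ = 0.3 / 0.5 / 0.7 | Against difference in change, ρ = 0.3 / 0.5 / 0.7 |
|---|---|---|
| 100% | 0.910 / 0.750 / 0.510 | 0.650 / 0.750 / 0.850 |
| 86% | 0.922 / 0.777 / 0.548 | 0.683 / 0.777 / 0.868 |
| 75% | 0.931 / 0.800 / 0.581 | 0.712 / 0.800 / 0.883 |

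Example at ρ = 0.5 and p = 0.86: 0.75/0.86 = 0.872; 0.872 + 0.25 = 1.122; 0.872/1.122 = 0.777. If a change score is the response, the ratio is (1+ρ)/2 at any p: 0.65, 0.75 and 0.85.

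**95% interval half-widths at ρ = 0.5**, from 1.96·√((2/95) × variance factor). The two free-mean contrasts coincide here because ρ² = (1−ρ)².

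- Complete: 0.284 to 0.246 SD
- 14% missing: 0.301 to 0.266 SD
- 25% missing: 0.318 to 0.284 SD

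**Unequal SDs**, with k = postoperative SD / preoperative SD and complete data. The ratio against the difference in change is k²(1−ρ²)/(k² + 1 − 2ρk). At ρ = 0.5:

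- k = 0.75: 0.422/0.8125 = 0.519
- k = 1.33: 1.327/1.439 = 0.922

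The ratio against the visit difference does not depend on k.

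**Checks.** Generalised least squares with four time points, compound symmetry and complete data gave the same complete-data ratios. A simulation of 6,000 trials (95 per group, ρ = 0.5, 14% missing) gave 0.781 and 0.782 against the 0.777 from the formula. All three estimators had mean error below 0.003 SD.

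**The case against.** The strongest reply is that the plan's model is valid, widely used and does what it was asked to do: it delivers both group differences and changes from the preoperative point. A more efficient specification for secondary outcomes without a power target is then an optional refinement. This stands as a limit on priority: the point concerns efficiency, and nothing stated in the plan is shown to fail.

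Four further objections have some force.

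- **Unknown size.** Correlation, SD ratio and clinical-score missingness are all absent from the documents. The gain could be as small as 7% (visit difference, ρ = 0.3, 25% missing) or 8% (difference in change, ρ = 0.5, k = 1.33, complete data). The direction does not depend on these values within the range shown.
- **Multiplicity.** The half-widths use 1.96, whereas the plan applies Bonferroni to the p-values. The absolute widths are therefore not those of a Bonferroni-adjusted analysis. A larger critical value multiplies both widths equally, so the relative gain is unchanged.
- **Timing.** The text is in the past tense, gives the observed CT missingness and reports that recruitment ended in February 2018. Data were probably in hand, which restricts the remedy to a labelled sensitivity analysis.
- **Population.** Intention-to-treat is defined for the primary outcome only. Randomisation justifies a common preoperative mean when the preoperative scores of all randomised patients stay in the model. Restriction to patients with follow-up would weaken that justification, so the population should be stated.

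**Conclusion.** The concern holds as a matter of efficiency on the secondary clinical outcomes. The specified fixed effects leave a collected preoperative score unadjusted on either reading of how it enters the model.

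A central illustration is ρ = 0.5 with equal SDs and complete data. The variance falls by 25%, equivalent to raising 95 per group to about 127 (95/0.75). With 14% or 25% of follow-up missing, the reduction is 22% or 20%. Over ρ from 0.3 to 0.7 and these missing fractions it runs from 7% to 49% against the visit difference and from 12% to 35% against the difference in change. With complete data and ρ = 0.5, an SD ratio between 0.75 and 1.33 moves the gain against the difference in change between 48% and 8%.

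These figures rest on assumed correlations, SD ratios and missingness. The change is worth making because it needs no new data.

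**What to change.** Keep the preoperative value as a response in the mixed model, but give both groups one common preoperative mean: the fixed effects become time plus group-by-postoperative-time. Report the group difference at each postoperative visit from that model. Within-group changes from the preoperative point remain available, and patients with only a preoperative score are retained.

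State explicitly how the preoperative value enters the model, and that the preoperative scores of all randomised patients are included. If results are already known, present this as a labelled sensitivity analysis beside the planned model, not as its replacement.

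The cost is one changed model statement and a short addition to the SAP text.
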